#### **14.7. Case Report Forms**

The study case report form (CRF) is the primary data collection instrument for the study. All data requested on the CRF must be recorded. All missing data must be explained. If a space on the CRF is left blank because the procedure was not done or the question was not asked, write "N/D". If the item is not applicable to the individual case, write "N/A".

#### **14.8. Records Retention**

Records relating to a specific research activity, including research records collected by investigators, must be maintained for at least three years after completion of the research (45 CFR 46.115(b); 21 CFR 56.115(b); 21 CFR 312.62). This minimum retention period applies whether or not any subjects were enrolled in the study.

If the research is FDA regulated, records should be retained for at least two years after approval of the investigational agent by FDA; if it is not approved, records should be retained at least two years after the study is terminated and FDA is notified (note the additional requirement below for clinical research studies).

Clinical records, including consent forms that document clinical intervention or clinical diagnostic procedure research-related procedures, must be retained in medical records by the institution for at least seven years, per CUMC and NYP policy which is based on state law.

## **15. STATISTICAL CONSIDERATIONS**

### **15.1. Statistical Analysis Plan Summary**

This statistical analysis plan was developed in collaboration with the study statistician, [name].

### **15.2. Populations for Statistical Analysis and Reporting**

#### **15.2.1 DLT Evaluable Population**

The DLT Evaluable Population consists of subjects in the initial 6 patient DLT cohort who complete at least 5 doses of azacitidine and 1 dose of pembrolizumab and completed the DLT observation period (6 weeks), and those who did not complete the DLT observation period and discontinued from study treatment due to a DLT event. The DLT Evaluable Population will be used for DLT assessments.

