### 1.1. Trial Design Overview

This is a single-arm, single-center, open-label trial of azacitidine combined with pembrolizumab in subjects with locally-advanced or metastatic pancreatic adenocarcinoma. Thirty-one evaluable subjects will be enrolled to assess the efficacy and safety of combination therapy in the second- line setting.

All subjects will have received systemic first-line chemotherapy, 5-FU or gemcitabine-based combination or monotherapy, prior to enrollment on the study. Azacitidine daily for 5 days will be given every 4 weeks (28 days). Fixed-dose pembrolizumab will be administered every 3 weeks for up to approximately 2 years beginning 2 weeks after initiation of azacitidine. The primary efficacy endpoint will be progression-free survival among all enrolled subjects. Disease progression will be determined based on RECIST 1.1 criteria; however, patients will be permitted to continue therapy following the development of progression of disease by RECIST 1.1 criteria if considered clinically appropriate by the study principal investigator.

As preliminary data suggests there is minimal toxicity overlap between pembrolizumab and a hypomethylating agent, there will be an accelerated Phase 1 dose determination component of the study. In the initial cohort, low-dose azacitidine will be administered, as studied in patients with advanced or metastatic solid tumors, and pembrolizumab will be administered at fixed dose

as detailed in the protocol. An initial cohort of 6 subjects will be enrolled, treated with combination therapy, and assessed for safety. Following enrollment of the initial 6 evaluable subjects all toxicity data will be reviewed. If 2 or more patients experience a treatment related dose-limiting toxicity (DLT) within the first 6 weeks of treatment administration (Defined in Section 5.2), then accrual at that dose level will stop. We will allow for 1 dose reduction in azacitidine and if agreed by the PI, the study will resume at the lower dose (Dose -1) and will again accrue 6 subjects who will receive combination therapy. If 2 or more subjects experience treatment related DLTs at this level, we will discontinue the combination study.

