## 5.2. Dose Limiting Toxicities

All toxicities will be graded according to the NCI CTCAE version 4.0 and assessed for relationship to study medications.

The incidence of DLT(s) assessed in the first 6 evaluable subjects during the first 6 weeks will be to initially determine whether the dose level of combination therapy is tolerable. A subject will be considered evaluable for DLT if they have received at least 1 dose of pembrolizumab after receiving the initial week of azacitidine. DLT should not be an AE considered by the investigator to be disease related. The following drug-related AE (whether related to one or both agents) will be considered a DLT:

- Any Grade  $\geq 3$  drug-related non-hematological AE, including the following laboratory abnormalities
  - If a subject has baseline Grade  $\leq 1$  AST, ALT, or total bilirubin, a drug-related Grade  $\geq 3$  toxicity will be considered a DLT
  - If a subject has baseline asymptomatic Grade 2 AST or ALT due to tumor infiltration in the liver, drug-related elevations in AST and/or ALT  $> 2x$  baseline or a maximum of  $> 8x$  ULN that does not resolve to Grade 2 or less within 48 hours (if symptomatic) or that does not resolve to Grade 1 or less within 3 weeks of onset (if asymptomatic) will be considered a DLT.
- Any Grade  $\geq 3$  drug-related non-hematological laboratory abnormality with the following exceptions:
  - Grade 3 abnormal laboratory result that is asymptomatic and lasts no longer than 72 hours.
  - Grade 4 lymphocytopenia not associated with symptoms or clinical manifestations
- Any toxicity managed by discontinuation of pembrolizumab (see [section 9.1](#)).
- Any toxicity managed by discontinuation of azacitidine (see [section 9.2](#)).
- Grade  $\geq 3$  thrombocytopenia with bleeding, and febrile neutropenia of any Grade.

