### **13.1.1 Definitions of evaluable subjects**

Evaluable for toxicity: All patients will be evaluable for toxicity from the time of their first treatment with azacitidine.

Evaluable for DLT assessment: The initial 6 subjects treated with at least 1 cycles (5 doses) of azacitidine and 1 dose of pembrolizumab will be evaluated for DLT. Subjects who do not complete these doses will be replaced.

Evaluable for PFS- primary outcome: All subjects who receive a single dose of pembrolizumab will be included in the primary outcome analysis of PFS. If subjects are removed from study prior to completing a single dose of pembrolizumab, they will be replaced.

Evaluable for objective response: Only those patients who have measurable disease present at baseline, have received at least one cycle of therapy, and have had their disease re-evaluated will be considered evaluable for response. These patients will have their response classified according to the definitions stated below. (Note: Patients who exhibit objective disease progression prior to the end of cycle 1 will also be considered evaluable.)

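### Sections 5.2, 13.1.1 and 15.2.1 define the DLT-evaluable subject differently, and each can leave an observed DLT out of the 2-of-6 safety count.

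*Combined protocol and SAP*

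**What the plan says.** The gate is in section 1.1: 6 subjects are treated, 2 or more treatment-related DLTs in the first 6 weeks stop the level, and at most 1 opens it to 25 more subjects. The same count at Dose -1 decides whether the combination study ends. Three sections say who is evaluable.

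- **5.2:** a subject is "evaluable for DLT if they have received at least 1 dose of pembrolizumab after receiving the initial week of azacitidine". Completion of the 6 weeks is not required.
- **13.1.1:** 5 azacitidine doses and 1 pembrolizumab dose. "Subjects who do not complete these doses will be replaced". There is no window condition and no exception for a DLT.
- **15.2.1:** either the same doses and the completed 6 weeks, or "those who did not complete the DLT observation period and discontinued from study treatment due to a DLT event". The second limb names no dose minimum. The section adds: "The DLT Evaluable Population will be used for DLT assessments".

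Under 5.2 a DLT may be due to either agent alone, and the list includes "Any toxicity managed by discontinuation of azacitidine". Pembrolizumab starts in week 3 (Table 3), so the first two weeks of the DLT window are azacitidine only.

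**The concern.** A safety gate should count every DLT seen in its window, whatever happens to the subject afterwards. Here the sections disagree on which subjects enter the count, and no other text reconciles them.

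1. **DLT before the required doses are complete.** Under 13.1.1 the subject is replaced, and under 5.2 the subject is not evaluable without a pembrolizumab dose. On its plain reading, the second limb of 15.2.1 counts a subject taken off treatment for that DLT.
2. **DLT managed by a hold, then early exit for another reason.** Neither limb of 15.2.1 fits. Sections 5.2 and 13.1.1 count the subject.
3. **No DLT and observation cut short.** Sections 5.2 and 13.1.1 accept the subject as DLT-free; 15.2.1 does not. No observed DLT is lost here, but the denominator of 6 means different things.

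With a threshold of 2 in 6, one subject can change the decision.

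**Working it through.** The plan gives no operating characteristics for the gate, so there is no stated figure to reproduce. First, the definitions side by side:

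| Subject | 5.2 | 13.1.1 | 15.2.1 |
|---|---|---|---|
| All treatment stopped for a DLT in weeks 1-2, no pembrolizumab | not counted | replaced | counted |
| Required doses, DLT held, exit before day 42 for another reason | counted | counted | not counted |
| Required doses, no DLT, exit before day 42 | counted as DLT-free | counted as DLT-free | not counted |
| Required doses, treatment stopped for a DLT | counted | counted | counted |
| Required doses, DLT, 6 weeks completed | counted | counted | counted |

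**How wide path 1 is.** Section 9.2 keeps pembrolizumab on schedule when the toxicity is not related to it. The path therefore needs azacitidine stopped within days 1-5, or all treatment stopped before week 3. If only azacitidine is stopped early and the 6 weeks are completed, 13.1.1 still replaces the subject, and neither limb of 15.2.1 clearly fits.

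**How wide path 2 is.** Holds are the rule for Grade 3 colitis (8.2.8) and other Grade 3 drug-related toxicity (Table 5). The DLTs listed as "thrombocytopenia with bleeding, and febrile neutropenia of any Grade" can also be handled this way, since 9.2 delays azacitidine for myelosuppression. Grade 3-4 hepatitis, pneumonitis, nephritis and myocarditis require discontinuation, so 15.2.1 keeps them. The exit must fall between about day 15 (first pembrolizumab) and day 42.

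**Size.** The true DLT rate p and all loss rates are assumptions. Pass means at most 1 DLT in 6: P(X ≤ 1) with X ~ Binomial(6, p').

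- *Every DLT counted, p' = p:* pass 65.5%, 35.8% and 23.3% at p = 0.20, 0.33 and 0.40.
- *Exactly 2 DLTs in 6:* 24.6%, 32.9% and 31.1% of cohorts. If one is left out and the subject replaced, the level passes when the replacement has no DLT, with probability about 1 - p: 80%, 67% and 60% instead of 0.
- *Path 1, share f of DLTs lost and replaced:* p' = p(1 - f)/(1 - pf). At p = 0.33 and f = 0.025, 0.05, 0.10, p' = 0.3244, 0.3188, 0.3071 and pass = 36.9%, 38.1%, 40.5%. At p = 0.20, pass = 66.5%, 67.5%, 69.5%.
- *Path 2, half of DLTs held, only held-DLT subjects lost, at 5% or 10%, and replaced:* f = 0.5 × 0.05 = 0.025 or 0.5 × 0.10 = 0.05. At p = 0.33, pass = 36.9% or 38.1%.
- *Path 2, DLT-free subjects lost at the same rate q and also replaced:* p' = p(1 - 0.5q)/[p(1 - 0.5q) + (1 - p)(1 - q)]. At p = 0.33 and q = 0.05, 0.10, pass falls to 34.6% or 33.4%. At p = 0.20 it falls from 65.5% to 64.5% or 63.4%.
- *Path 3, upper bound (every missed DLT would have come after the exit), early-exit rate q:* p' = p(1 - q). At p = 0.33 and q = 0.05, 0.10, pass is at most 39.1% or 42.7%.

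Replacement is stated in 13.1.1 for path 1. For path 2 it is only implied by the need for 6 evaluable subjects.

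**The case against.** The strongest reply is that section 1.1 is itself the gate. Its stop sentence speaks of patients, not evaluable patients, and it follows this instruction: "Following enrollment of the initial 6 evaluable subjects all toxicity data will be reviewed". On that reading, six evaluable subjects only set the time of the review, and a replaced subject with a DLT still counts. This is a fair reading, but 5.2 assesses DLT incidence in the first 6 evaluable subjects and 15.2.1 ties DLT assessment to its own population. The text supports both, which is the problem.

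Both omission paths are also narrow. Path 1 is not the default course under 9.2. Path 2 is uncommon: AEs are collected for 30 days after treatment stops, so a subject who stops for progression just after day 15 is normally still observed to about day 45. Cancer death, consent withdrawal and loss to follow-up remain, in a population entering with ECOG 0-1 and a life expectancy above 3 months. The Safety Population, DSMC review and the aggregate-toxicity rule in 13.8 are further backstops, though none of them sets the gate count.

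A reader might infer two stronger claims. One is that every azacitidine DLT in weeks 1-2 is dropped; 9.2 contradicts that. The other is that 15.2.1 biases the gate toward passing. The documents do not support that either, because 15.2.1 also removes DLT-free early leavers, and with equal loss the pass probability falls.

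**Conclusion.** The conflict is in the current text and stands as a minor point. Sections 13.1.1 and 15.2.1 can each drop a DLT that the other keeps, and 5.2 sides with 13.1.1 where no pembrolizumab was given. What matters is the single cohort with exactly 2 DLTs, where one omission replaces a stop with a possible go for 25 more subjects. On average the effect is a few percentage points at most under the assumed losses, and for a held DLT followed by early exit its sign depends on who else leaves early. The documents give neither DLT rates nor loss rates, so the percentages are illustrations. Path 1 rests on not reading the dose minimum of the first limb of 15.2.1 into the second. If it were read in, the conflict on that path would disappear, but all three sections would then miss the DLT of a subject who stopped before pembrolizumab. PFS is not affected, because the efficacy population in 15.2.3 does not use DLT evaluability.

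**What to change.** Put one definition in 5.2, 13.1.1 and 15.2.1, applied to each 6-subject cohort (starting dose and, if opened, Dose -1). Every treated subject with a DLT as defined in 5.2 within 6 weeks counts, whatever doses were received and whatever the reason for leaving. A subject without a DLT counts only if the required doses and the 6 weeks are completed; otherwise the subject is replaced.

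This is wording in three sections. No dose or toxicity-management rule changes. The real cost is that a level fails slightly more often when there is early loss, because subjects with a DLT always count while DLT-free early leavers are replaced. With equal early loss q, p' = p/[p + (1 - p)(1 - q)]. For q = 5% or 10%, the pass probability goes from 35.8% to 33.5% or 31.2% at a 33% DLT rate, and from 65.5% to 63.5% or 61.3% at a 20% rate. For a safety gate that is the cautious direction.

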#### **15.2.2 Safety Population**

The Safety Population consists of all subjects treated with at least one dose of any study drug. The Safety Population for azacitidine consists of all subjects treated with at least one dose of azacitidine, and will be used for the analysis of the safety data. The Safety Population for pembrolizumab consists of all subjects treated with at least one dose of pembrolizumab, and will be used for the analysis of the safety data.

#### **15.2.3 Efficacy Population**

Evaluable for PFS- primary outcome: All subjects who receive a single dose of protocol therapy will be included in the primary outcome analysis of PFS. If subjects are removed from study prior to completing a single dose of pembrolizumab, they will be replaced but will be included in the primary analysis.

Evaluable for objective response: Only those patients who have measurable disease present at baseline, have received at least one cycle of therapy, and have had their disease re-evaluated

will be considered evaluable for response. These patients will have their response classified according to the definitions stated below. (Note: Patients who exhibit objective disease progression prior to the end of cycle 1 will also be considered evaluable.)

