### 6.4. Subject Recruitment

This study will be conducted at Columbia University Medical Center. Thirty-one patients will be needed to meet the primary study endpoint. The amount of time required to complete this trial will depend on the rapidity of accrual. We estimate evaluation of 3-5 subjects a month in our center with enrollment of 2 subjects a month to complete accrual over 16-18 months with an anticipated 4-6 week pause after enrolling the 6th subject for safety analysis. If the first dose level is deemed intolerable ( $\geq 2$  DLTs), we will accrue 6 subjects at a lower dose level and complete 31 subjects (25 additional) at that dose level. Thus the maximum number of subjects enrolled in this study will be 37.

Participation is voluntary. The patient must be aware of the neoplastic nature of his/her disease and willingly consent after being informed of the procedures to be followed, the

experimental nature of the therapy, alternatives, potential benefits, side effects, risks, and discomforts. The investigator will make certain that an appropriate informed consent process is in place to ensure that potential research subjects, or their authorized representatives, are fully informed about the nature and objectives of the clinical study, the potential risks and benefits of study participation and their rights as research subjects.

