#### **15.4. Size/Accrual Rate**

A total of 31 subjects will be enrolled over 18 months with plan to screen 4-5 subjects in our

multi-disciplinary pancreas clinic each month with enrollment of 2-3 patients per month. If the original 6 patient DLT cohort requires a dose reduction then up to a maximum of 37 subjects will be enrolled with 31 additional enrolled at the final dose level.

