### **15.7. Analysis Populations**

All subjects who received at least one dose of study treatment will be included in the primary and secondary efficacy and safety analysis as detailed in [Section 15.2](#).

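### If the run-in leads to a lower azacitidine dose level, the primary PFS set as written pools subjects enrolled at two dose levels, nominally 37 instead of the planned 31

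*Combined protocol and SAP*

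**What the plan says.** **Who is analysed.** Section 15.2.3 states: "All subjects who receive a single dose of protocol therapy will be included in the primary outcome analysis of PFS". It adds that subjects removed before a pembrolizumab dose are replaced but stay in the primary analysis. Section 15.7 repeats the rule: "All subjects who received at least one dose of study treatment will be included in the primary and secondary efficacy and safety analysis". The design overview (1.1) is wider still: "The primary efficacy endpoint will be progression-free survival among all enrolled subjects". Section 13.1.1 has a different entry condition: "All subjects who receive a single dose of pembrolizumab will be included in the primary outcome analysis of PFS". None of the four mentions dose level.

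**How many are planned.** Section 1.1 stops accrual at the first dose level if 2 or more of the initial 6 subjects have a DLT, and allows one azacitidine reduction. Table 6 gives the levels as 50 and 40 mg/m², with pembrolizumab unchanged. For that case section 6.4 says "we will accrue 6 subjects at a lower dose level and complete 31 subjects (25 additional) at that dose level", and section 15.4 says "up to a maximum of 37 subjects will be enrolled with 31 additional enrolled at the final dose level". Sections 5.3 and 15.2.5 state the sample size and power for 31.

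**Subset analyses.** Section 15.2.4 bases all conclusions on all eligible patients and does not let sub-analyses support efficacy conclusions.

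**The concern.** The sample-size sections treat the 31 subjects at the final dose level as the ones who answer the primary question. The analysis-set sections do not. If the dose level is reduced, they add everyone enrolled at the level that was left because of DLTs. The reported PFS would then describe a mixture of two cohort dose levels, not the regimen carried forward, and the set would differ from the one for which power is stated.

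No section restricts the primary set to the final level, plans PFS by dose level, or says what becomes of the first cohort's PFS data. The trial is open-label with a historical control. If the rule is not settled beforehand, the choice between 31 and 37 could be made after the PFS data are known.

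**Working it through.** **1. The plan's own count.** At the lower level, 6 + 25 = 31 (6.4). Adding the first cohort, 6 + 31 = 37, the maximum in 6.4 and 15.4. So the first 6 do not count toward the 31.

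**2. What each analysis rule does with the first 6.**
- 15.2.3, 15.7 and 1.1: included, because they were enrolled and treated.
- 13.1.1: also included. To be DLT-evaluable a subject needs 5 azacitidine doses and one pembrolizumab dose, so each of the 6 has had pembrolizumab.

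The primary set is therefore nominally 37, and 6/37 = 16.2% come from the earlier level. Six is a minimum. Subjects not evaluable for DLT are replaced (13.1.1), but under 15.2.3 they stay in the set once they have had one dose.

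**3. Chance that this branch occurs.** P(2 or more DLTs in 6) = 1 − (1−p)^6 − 6p(1−p)^5. The documents give no DLT rate, so p is assumed.

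| True DLT rate p | Chance of reduction |
|---|---|
| 10% | 11.4% |
| 20% | 34.5% |
| 30% | 58.0% |

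**4. Illustrative effect on the primary result.** From 15.2.5: historical median 2 months, target 4 months, one-sided alpha 0.05, 18 months' accrual plus 6 months' follow-up. Assumed: exponential PFS; the 6 enter in months 0–3 and the 31 in months 3–18; analysis at month 24; one-sample log-rank test. The statistic is Z = (O − E)/√E with E = Σ(follow-up time × ln 2/2), and the result is positive if Z < −1.645. There were 200,000 simulated trials per row.

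| Final dose median (31) | First dose median (6) | Chance of a positive result |
|---|---|---|
| 2 | none (31 alone) | 3.8% |
| 2 | 2 | 3.9% |
| 2 | 2.2 | 5.0% |
| 2 | 2.5 | 6.8% |
| 2 | 3 | 10.8% |
| 2 | 4 | 22% |
| 4 | none (31 alone) | 97% |
| 4 | 2 | 96% |

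Hand check of the 22% row: the 31 contribute O ≈ E ≈ 30.3. The 6 contribute O ≈ 5.9 and, at half the null hazard, E ≈ 5.9/0.5 = 11.8. Then Z ≈ (36.1 − 42.0)/√42.0 = −0.91 on average. With unit variance, the chance of falling below −1.645 is about 23%.

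**5. Effect on the estimate.** With the final dose at 4 months and the first at 2, the pooled median solves (6/37)·0.5^(t/2) + (31/37)·0.5^(t/4) = 0.5, giving t = 3.55, a fall of 0.45 months. The exponential estimate falls from 4.04 to 3.66, or 0.38 months.

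**Note on power.** The 97% for 31 subjects exceeds the plan's 80% because a one-sample calculation needs only about 13 events. The plan does not state its method. A two-group Freedman calculation (56 events, about 30 per group) comes close to 31. This does not affect the point about dose levels.

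**The case against.** The strongest reply is that the practical effect is probably small. The step is 50 to 40 mg/m² of one agent, a 20% change (10/50), with the other agent unchanged. A reader might infer from the bottom of the false-positive range that pooling would lift the error rate to 20% or more. The documents do not support that. It needs a twofold difference in median PFS between the two levels, which is the whole effect the trial hypothesises. With a first-dose median of 2.2 to 3 months the rate is about 5% to 11%. This part of the objection stands.

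A reader might also infer that six subjects could tip the conclusion in either direction. In the downward case power goes only from 97% to 96%, so the cost there is to the estimate and hardly to the decision. Nor do the documents say that either dose level is the wrong one, and this point does not depend on that.

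Further points against:
- The issue arises only after 2 or more DLTs, and 1.1 makes resumption depend on the principal investigator's agreement.
- Section 8.2.2 allows individual azacitidine reductions. Exposure is therefore mixed in any case, and some first-cohort subjects may move to 40 mg/m². This softens the contrast but does not remove the pooling by cohort.
- An all-treated set is a sound default, and extra subjects do not reduce power. That holds within one regimen. It does not explain why 6.4 and 15.4 take the trouble to reach 31 at the final level.
- Section 15.2.4 is aimed mainly at protocol deviations. Read literally, though, it would also stop a final-dose result from supporting the efficacy conclusion.

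**Conclusion.** The point holds. It is a conflict between stated rules and not merely a missing detail: the analysis-set sections pool two cohort dose levels, while the sample-size sections plan 31 subjects at the final one. The composition is certain once a reduction occurs: nominally 37 subjects, at least 6 of them (16%) enrolled at the earlier level. The chance of a reduction rests on assumed DLT rates. The bias figures rest on an assumed test, exponential PFS, an assumed accrual pattern and assumed medians by dose, so they show a range and not a forecast. The plan should be changed because the cost is very small and the rule needs to be fixed before PFS is known. It is not a threat to the trial if no reduction occurs.

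**What to change.** In section 15.2.3 add:

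> If the cohort azacitidine dose level is reduced, the primary PFS analysis includes all treated subjects enrolled at the final dose level, classified by the dose level assigned at enrolment regardless of later individual reductions. All subjects enrolled at the earlier dose level, including any who were replaced, are reported separately and added in a pooled sensitivity analysis.

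Classifying by assigned level keeps a first-cohort subject who is later reduced under 8.2.2 from being counted at the final level. Referring to all subjects at the earlier level, and not to the first 6, covers those replaced.

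One sentence in 15.2.3 is not enough by itself. Sections 1.1, 13.1.1, 15.4 and 15.7 should point to the same definition, and 15.2.4 should say that the final-dose set is the primary set and not a sub-analysis.

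The cost is a short text amendment. No extra subjects are needed, no treatment rule changes, and the planned 31 is kept. The small downside is that subjects at the earlier level no longer contribute to the primary estimate.

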#### **15.2.4 Reporting of Outcomes**

All conclusions should be based on all eligible patients. Sub analyses may then be performed on the basis of a subset of patients, excluding those for whom major protocol deviations have been identified (e.g., early death due to other reasons, early discontinuation of treatment, major protocol violations, etc.). However, these sub analyses may not serve as the basis for drawing conclusions concerning treatment efficacy, and the reasons for excluding patients from the analysis should be clearly reported. The 95% confidence intervals should also be provided.

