#### **15.2.6 Secondary Endpoints**

The secondary hypothesis of this study is that combination therapy will lead to improvements in overall response rate (ORR), duration of response (DOR), disease control rate (DCR), and overall survival (OS). These will all be reported with percentages and 95% confidence intervals. The Kaplan-Meir method will be used to evaluate all time to event endpoints.

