##### **15.2.6.1 Definition of secondary endpoints:**

###### **▪ Objective Response Rate**

- ORR is defined as the proportion of the subjects in the analysis population who have a CR or PR. Responses are based on assessments per RECIST 1.1 as described in Section 13.4.

- **Duration of Response**
  - For subjects who demonstrate CR or PR, based on assessments per RECIST 1.1, DOR is defined as the time from first documented evidence of CR or PR until disease progression or death due to any cause, whichever occurs first.
- **Disease Control Rate**
  - DCR is defined as the percentage of subjects who have achieved CR, PR, or SD based on assessments per RECIST 1.1.
- **Overall Survival (OS)**
  - OS is defined as the time from first dose of study medication to death due to any cause.

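### The plan gives conflicting populations for ORR and DCR, and the set written for response drops treated subjects who are never re-evaluated, which can only raise the rate or leave it unchanged

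*Combined protocol and SAP*

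**What the plan says.** Two sections define a response set in the same terms. Section 15.2.3 (Efficacy Population) admits "Only those patients who have measurable disease present at baseline, have received at least one cycle of therapy, and have had their disease re-evaluated". Section 13.1.1 (Definitions of evaluable subjects) begins the same rule: "Evaluable for objective response: Only those patients who have measurable disease present at baseline". Both add one exception, for objective progression before cycle 1 ends.

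Other sections point to wider sets:

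- Section 15.2.4 (Reporting of Outcomes): "All conclusions should be based on all eligible patients". It then allows subset analyses that leave out patients with major deviations, and its examples include early death from other causes and early discontinuation. It bars efficacy conclusions from such subsets and asks for the reasons for exclusion.
- Section 15.7 states: "All subjects who received at least one dose of study treatment will be included in the primary and secondary efficacy and safety analysis". It points to section 15.2 for the detail.
- For PFS, section 15.2.3 takes everyone with one dose of protocol therapy. Of subjects removed before pembrolizumab it says "they will be replaced but will be included in the primary analysis".

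The endpoint definitions (15.2.6.1, repeated in 13.6.1.2) do not choose between these sets. For response: "ORR is defined as the proportion of the subjects in the analysis population who have a CR or PR". For disease control: "DCR is defined as the percentage of subjects who have achieved CR, PR, or SD". On reporting, section 15.2.6 says: "These will all be reported with percentages and 95% confidence intervals".

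**The concern.** Two analysts could each follow the text and report ORR and DCR on different denominators from the same data. The trial is open-label with a single arm, so a denominator not fixed in advance can be chosen once the results are known.

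The choice is also not neutral. The set written specifically for response removes treated subjects who have no follow-up assessment. Such subjects can never add to the numerator.

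The rates will be read. Section 3.10 singles out ORR and OS among the additional efficacy endpoints. Section 2.2 hypothesises high response rates and better disease control than historical controls. DCR also enters an exploratory Fisher's exact comparison between methylation groups (15.2.7).

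**Working it through.** The plan gives no expected rate, sample size or power for ORR or DCR, so there is no stated figure to reproduce. The check is a comparison of the text, followed by the size of the effect.

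**1. Who is in each set**

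| Source | Set | Treated subject, no re-evaluation, no early objective progression |
|---|---|---|
| 13.1.1 and 15.2.3, response | Measurable disease, one cycle, re-evaluated | Out |
| 15.2.4 | All eligible patients | In, if eligible |
| 15.7 | All dosed, with detail left to 15.2 | In, unless 15.2.3 overrides |
| 15.2.6.1, ORR | An unnamed analysis population | Not settled |
| 15.2.6.1, DCR | No set named | Not settled |

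The pointer from 15.7 does not resolve this, because section 15.2 holds both the restricted set (15.2.3) and the all-eligible rule (15.2.4).

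**2. What each condition removes**

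- Measurable disease: no eligible subject, because section 6.1 already requires it.
- Re-evaluation: subjects who cannot be classed as CR, PR or SD. Death or clinical deterioration without a scan is not covered by the exception, which needs objective progression.
- At least one cycle: no fixed direction, because a subject short of one cycle could still have been scanned and have any outcome.

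**3. Size of the re-evaluation effect**

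Let x be the number of responders (or of subjects with disease control), N the dosed subjects and k those never re-evaluated. Assume the one-cycle condition removes nobody else.

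- All dosed: x/N. Response-evaluable: x/(N-k). Ratio: N/(N-k), which is never below 1.
- N = 31, k = 0: 31/31 = 1.00
- N = 31, k = 3: 31/28 = 1.11
- N = 31, k = 6: 31/25 = 1.24
- N = 34 (31 plus an assumed 3 replaced subjects): 34/31 = 1.10 at k = 3 and 34/28 = 1.21 at k = 6

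**4. Illustration with exact (Clopper-Pearson) 95% intervals, N = 31**

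The counts x and k are assumptions.

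| x | k = 0 | k = 3 | k = 6 |
|---|---|---|---|
| 8 (disease control) | 8/31 = 26% (12-45%) | 8/28 = 29% (13-49%) | 8/25 = 32% (15-54%) |
| 2 (response) | 2/31 = 6.5% (0.8-21%) | 2/28 = 7.1% (0.9-24%) | 2/25 = 8.0% (1.0-26%) |

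With no responders ORR stays at 0% and only the upper limit moves, from 11% (0/31) to 14% (0/25).

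**5. What bears on k**

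The first on-study scan is at 8 weeks. Footnote l of the flow chart plans imaging at discontinuation for subjects without confirmed progression, and 6.6.2 continues imaging every 8 weeks off treatment. Both keep k down. Neither forces it to zero: footnote l waives the scan if one was taken in the preceding 4 weeks. Screening imaging may be up to 28 days old at first dose, so for a very early discontinuer the baseline scan might satisfy the waiver.

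**The case against.** The best defence is that 15.2.3 is the specific rule. It sits under the efficacy-population heading, it addresses objective response, and 15.7 defers to 15.2. For ORR that is a reasonable reading, and a response-evaluable denominator is then partly a design preference. It does not close the matter. On that reading 15.7 would not hold for ORR, 15.2.4 lies in the same section and says something else, and nothing ties DCR to the restricted set.

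Second, 15.2.4 already bars efficacy conclusions from subsets and asks for reasons for exclusion. This stands and limits the harm. But those subsets are framed around major protocol deviations, which a missing scan need not be, and the section still names no denominator for either rate.

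Third, k is probably small. Eligibility requires ECOG 0-1 and a life expectancy above 3 months, and scans are planned at discontinuation. Even at k = 6 the intervals overlap almost completely. This also stands.

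A reader might infer more than the documents support:

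- **That a quarter to a half of subjects would drop out.** Week 8 is 56/30.4375 = 1.84 months. With exponential PFS, the share with an event by then is 1 - 0.5^(1.84/2) = 47% at a 2-month median and 1 - 0.5^(1.84/4) = 27% at 4 months. These are PFS events, not unscanned subjects. Progression seen on a scan is a re-evaluation. The minimum of 20 on-treatment biopsies in 15.2.7 is not a count of re-evaluated subjects either.
- **That the unscanned are mainly early deaths or patients too ill to scan.** The plan does not say so. Withdrawal of consent and loss to follow-up also leave subjects unscanned.
- **That subjects replaced before pembrolizumab have no place in the response analysis.** Taken literally, 15.7 includes every dosed subject in the secondary efficacy analyses.
- **That N = 37 is the relevant total after a dose reduction.** Sections 6.4 and 15.4 give 37 as an enrolment maximum. They do not say that dose levels are pooled for response.

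**Conclusion.** The inconsistency is real and should be corrected. Two readings of the plan give different denominators for ORR and DCR. The set written for response excludes treated subjects who could only count as failures. The re-evaluation exclusion therefore raises the rate by N/(N-k) or leaves it unchanged, and the effect is zero if everyone is re-evaluated. The size depends on k, which the plan does not give.

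The consequence is limited to ORR, DCR and the exploratory comparison that uses DCR. Neither rate has a reference value or a decision rule. The primary PFS analysis and its power are not affected. The documents do not support a claim that the plan will report inflated rates: that would require both the 15.2.3 set to be the one used and k to be above zero.

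**What to change.** In 15.2.3, 15.2.6.1 and 15.7, and in the matching 13.1.1 and 13.6.1.2:

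- State that ORR and DCR use the same set as the PFS analysis in 15.2.3 and 15.7: all subjects with at least one dose of protocol therapy, including those replaced before pembrolizumab. Refer to 15.2.3 for this set, because 13.1.1 ties PFS evaluability to a pembrolizumab dose.
- Count a subject with no post-baseline assessment as a non-responder and as not having disease control.
- Keep the response-evaluable set as a labelled sensitivity analysis. Report how many subjects were never re-evaluated and why. Say which cycle its one-cycle condition means, since the flow chart uses 4-week azacitidine and 3-week pembrolizumab cycles.

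Also reconcile the all-eligible rule in 15.2.4 with this dosed set, so that a dosed but ineligible subject is handled the same way for PFS, ORR and DCR.

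The cost is wording only, with no new data. Reported rates may be slightly lower. The sensitivity set stays available for comparison with historical rates based on an evaluable denominator.
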